5.2 Safety outcomes

According to their potential association with the treatment, AEs will be categorized as treatment-related or non-treatment-related within 24 hours after their occurrence. Treatment-related adverse events include pain, haematoma, localized infection, broken needle, fainting, nausea, headache, dizziness, insomnia, vomiting, or palpitations during or after treatment.

Serious adverse events will be defined as events requiring hospitalization, causing disability or impaired ability to work, threatening life or resulting in death.

All the adverse events and serious adverse events, whether related to acupuncture or not, will be reported and documented.

6. Statistical Considerations

6.1 Study hypothesis

The primary study hypothesis is that acupuncture is more effective than sham acupuncture in relieving symptoms of CP/CPPS.

6.2 Study Populations

All patients with randomization will be included in the analysis set regardless of whether they receive any treatment. According to the intention-to-treat principle, all analysis will be based on the randomization set.

6.3 Statistical Analyses

6.3.1 The general principle

Summary Statistics

Summary tables (descriptive statistics and/or frequency tables) will be provided for all variables at different endpoints. For continuous variables, means and standard deviations will be presented, unless the variable has a skewed distribution, in which case medians, 25th and 75th percentiles will be presented. For categorical variables, the number and percentage of participants within each category will be presented. For each variable (continuous or categorical), the number of missing values will be reported.

Statistical Comparisons Between Groups

Continuous variables will be compared using a two-sample t-test or Wilcoxon rank-sum test if data show serious deviations from a normal distribution. Categorical data or ordinal data will be compared using a Wilcoxon rank-sum test, chi-square test or Fisher’s exact test, as appropriate. All tests will be two-sided.

For the analysis of the primary and secondary outcomes, estimated treatment differences and associated 95% two-sided confidence intervals will be presented.

Multiple Comparisons

Since only one co-primary outcome is defined, no adjustments to the significance level will be required to account for multiple testing.

For the analysis of the secondary and safety outcomes, no adjustment for multiple comparisons will be made.

Analysis Software

For all statistical analyses, SAS 9.4 software will be used. All hypothesis testing will be carried out at the 5% (2-sided) significance level.

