3.4 Study Time Frame

The duration of the study for each participant will be 34 weeks: 2 weeks before randomization as eligibility screening and baseline assessment, 8 weeks of treatment period, and 24 weeks of follow up period after the cessation of treatment (Figure 1. Study Design).

[figure not shown]

Figure 1. Study Design

There will be twelve clinical visits:

Visit 1 will be scheduled during weeks -1 and -2 as eligibility screening and baseline assessment;

Visit 2 will be scheduled for baseline assessment and randomization;

Visits 3-10 (20 sessions of treatments) will be scheduled for the 8-week treatment period;

Visits 11 and 12 will be scheduled at weeks 20 and 32, respectively, during 24-week follow-up period.

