8.2.4 Twenty-four-week Follow-up Phase

During the 24-week follow-up (weeks 9-32), Visit 11 will be scheduled at week 20, and Visit 32 will be scheduled at week 32.

Participants will complete the NIH-CPSI, IPSS, GRA, IIEF-5, HADS and EQ-5D-5L at weeks 20 and 32. Urinary flow rate will be completed at week 32.

For the results of Visit 11 (week 20), the notebook could be mailed to hospitals or submit to hospitals by participants in person. At weeks 32, participants need to visit the hospital in person for the examination of urinary flow rate, therefore they will bring the notebook to hospital by themselves.

9. Safety Assessment and Subject Withdrawal

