11.1 Sample Size Calculations

Sample-size calculations were based on 90% power to detect a difference of 17% between response rates in the two groups (63.7% in the acupuncture group compared with 46.7% in the control group) for the primary outcome, defined as a decline of 6 or more points in the NIH-CPSI total score²¹. These values are equivalent to an odds ratio of 2.0. On the basis of a two-sided alpha level of 0.05, we calculated that a sample of 440 participants will be required (220 in each group). This proposed sample size includes a 15% increase to account for dropouts. To control for type I error, the two time points in the primary outcomes will have to be positive in order for the trial to prove the efficacy of acupuncture.

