5.1 Efficacy outcomes

5.1.1 Primary Outcomes

The two co-primary outcomes include the proportions of responders at week 8 and week 32. The responder is defined as a participant with a decline of 6 points or more from baseline in the total score of the Chinese version NIH-CPSI. As a validated, self-reported questionnaire, NIH-CPSI is widely used to assess CP/CPPS symptoms^{28, 29}. NIH-CPSI consists of 9 items divided into 3 discrete domains: pain (0–21 points), urinary symptoms (0–10 points) and QoL (0–12 points), with a total score of 0–43 points (a higher score indicates worse symptoms). A decline of at least 6 points in NIH-CPSI has been identified as the minimal clinically important difference (MCID)²⁵.

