6.3.3 Analyses for Primary Outcome

Primary outcome analysis will be conducted with a logistic generalized linear mixed model (GLMM) for repeated measures. Responder or non-responder at each scheduled post-baseline visit (end of treatment, and 20 and 24 weeks after treatment) is the dependent variable. Subjects who discontinue without providing the NIH-CPSI score will be considered as non-responders. The logistic GLMM is fitted using the logit link and the binomial distribution. The model will include the baseline NIH-CPSI total score as a fixed-effect covariate, with treatment group (acupuncture and sham acupuncture), visit and treatment \times visit interaction as fixed-effect categorical factors. The interaction will remain in the model regardless of significance. Treatment group comparisons at each visit will be estimated by differences between least squares means from the treatment \times visit interaction, and will be presented as odds ratios with accompanying *p* values and 95% CIs. The predicted probability of response at each visit will also be presented. Such models provide fairly robust results for treatment comparisons when longitudinal binary responses are missing, with an assumption that data are missing at random(MAR), according to reported values³⁶.

Sensitivity Analyses for the Primary Outcome

Because the MAR assumption cannot be verified using the data, the sensitivity of inferences to departures from the MAR assumption should be tested³⁷. A straightforward sensitivity analysis for the MAR assumption in multiple imputation is based on the control-based pattern imputation model under the MNAR assumption by using the SAS procedure Proc MI process. Therefore, mixed-effect model under MNAR assumption will be used. 6.3.4 Analyses for Secondary Outcome

Efficacy analyses for all secondary outcomes will be performed in the ITT population, without imputation of missing data.

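### Does miscounting the co-primary outcomes in SAP 6.3.1, and mislabelling the week-20 visit in 6.3.3, undermine the primary analysis?

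*Combined protocol and SAP*

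**What the plan says.** SAP 5.1.1 defines the primary endpoint: "The two co-primary outcomes include the proportions of responders at week 8 and week 32". Protocol 8.1.1 uses the same words.

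Under Multiple Comparisons, SAP 6.3.1 then states: "Since only one co-primary outcome is defined, no adjustments to the significance level will be required to account for multiple testing". Later in that section it sets the level: "All hypothesis testing will be carried out at the 5% (2-sided) significance level".

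The success rule is in protocol 11.1, not in the SAP: "To control for type I error, the two time points in the primary outcomes will have to be positive" before the trial can be said to have shown efficacy.

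SAP 6.3.3 fits a logistic mixed model to responder status at the scheduled post-baseline visits, which it lists as "end of treatment, and 20 and 24 weeks after treatment". It adds: "Treatment group comparisons at each visit will be estimated by differences between least squares means", taken from the treatment-by-visit interaction.

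On timing, protocol 3.4 says "Visits 11 and 12 will be scheduled at weeks 20 and 32, respectively, during 24-week follow-up period", and protocol 8.2.4 says "During the 24-week follow-up (weeks 9-32), Visit 11 will be scheduled at week 20". SAP 5.1.2 places the follow-up NIH-CPSI at weeks 20 and 32 and makes response at week 20 a secondary outcome.

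**The concern.** A statement about multiplicity should rest on a correct count of the primary tests, and this one does not. Someone with the SAP alone sees two co-primary outcomes in 5.1.1, one in 6.3.1, both tested at 5%, and nothing saying whether one positive result would be enough. If one were enough, two unadjusted tests would inflate the type I error. Protocol 11.2 makes the SAP the place where planned analyses are defined, so one would look for the success rule there.

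The visit label is also awkwardly placed, because it sits in the definition of the primary model's dependent variable. Read literally, it asks for a responder status at a time when nobody is assessed. SAP 6.3.3 also reports a comparison at every modelled visit without repeating which of them are primary. At stake would be the trial's false-positive rate and the data that enter the primary model.

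**Working it through.** **1. The plan's own sample size.** Protocol 11.1 gives 63.7% against 46.7%, 90% power, two-sided alpha 0.05, 15% added for dropout, and 440 participants (220 per group). The usual two-proportion formula gives

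n = [1.960·√(2 × 0.552 × 0.448) + 1.282·√(0.637 × 0.363 + 0.467 × 0.533)]² / 0.17² = 178 per group, or 190 with a continuity correction.

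From 190, 190 × 1.15 gives 219 per group (438 in total), and 190 / 0.85 gives 224 per group (448). The stated 440 lies between them. The formula used is not stated, and without the correction the totals are 410 to 420. Splitting alpha to 0.025 per test would give 211 per group without the correction, hence 243 to 249 per group after dropout (486 to 498 in total). So the sample size was built on the full 5% for each test, as the both-positive rule allows.

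**2. False claims under the both-positive rule.** Each test is two-sided at 5%, so it favours acupuncture wrongly with probability 0.025 when there is no effect. A claim needs both tests to succeed. If at least one time point has no effect, then

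P(claim) ≤ P(the test at that time point succeeds) = 0.025.

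This bound needs no assumption about correlation. The rates below it do, and the documents give no correlation, so a range is shown (bivariate normal, critical value 1.96):

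| Correlation (assumed) | No effect at either time point | 90% power at one, no effect at the other |
|---|---|---|
| 0 | 0.0006 | 0.0225 |
| 0.5 | 0.0046 | 0.0249 |
| 0.7 | 0.0083 | 0.0250 |
| 0.9 | 0.0148 | 0.0250 |

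Check at correlation 0: 0.025 × 0.025 = 0.0006, and 0.90 × 0.025 = 0.0225. For 90% power the mean z is 1.960 + 1.282 = 3.242.

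**3. The reading that would do harm.** If either time point alone could carry the claim, the two-sided family-wise error would be 1 − 0.95² = 0.0975 at correlation 0 and 0.070 at correlation 0.9. Protocol 11.1 excludes that reading, and nothing in the SAP permits it.

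**4. Visit timing.** Treatment ends at week 8.

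- Study week 20: 20 − 8 = 12 weeks after treatment. SAP 6.3.3 says 20, which is 8 weeks out.
- Study week 32: 32 − 8 = 24 weeks after treatment. SAP 6.3.3 agrees.
- Twenty weeks after treatment would be 8 + 20 = week 28, when no visit and no NIH-CPSI is scheduled.

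The list in SAP 6.3.3 has three entries and begins at the end of treatment. The schedule has exactly three NIH-CPSI assessments from that point on: weeks 8, 20 and 32. The entry marked 20 can only be study week 20, written on the wrong time scale.

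**5. Which contrasts are primary.** SAP 5.1.1 names weeks 8 and 32, and SAP 5.1.2 lists week 20 as secondary. Reporting a contrast at every modelled visit is normal for a repeated-measures model and does not promote week 20.

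**The case for a change.** The strongest case for a change is that the sentence in SAP 6.3.1 is not just loosely worded. It is the stated ground for a multiplicity decision, and on the plan's own definitions the count is wrong. Reading it as one co-primary pair with a single success claim is possible, since protocol 11.1 itself moves between a single primary outcome and two time points. That reading does not remove the literal conflict with SAP 5.1.1, and even one pair could not be tested unadjusted without the both-positive rule, which the SAP does not restate. Correcting both passages would take a few words and cost no patients or data.

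All of that stands as a description of the text. What it does not show is a consequence. The rule is pre-specified in the protocol, with control of type I error given as its purpose, and the SAP nowhere contradicts it. The week-20 entry has only one assessment it can refer to. An analyst holding both documents would test the same two contrasts at the same level on the same data, whether or not the wording was tidied.

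**Conclusion.** Both inconsistencies are real, and both are clerical. Leaving the two tests unadjusted is correct because protocol 11.1 requires both to be positive. The false-claim rate is then at most 2.5% whatever the correlation between the tests, and 0.06% to 1.5% if acupuncture has no effect at either time point and the correlation lies between 0 and 0.9. The visit label is 8 weeks out for one of three modelled visits, has no data at the literal date to be confused with, and touches neither co-primary time point. The primary contrasts are fixed in SAP 5.1.1.

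This conclusion rests on reading the protocol and SAP together, so that the success rule in protocol 11.1 governs the analysis. On that basis no test, significance level, sample size or estimate would differ, and no change to the plan is called for.

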6.3.2 Demographics and Baseline Characteristics

All data recorded at baseline will be summarized by group. Comparisons between groups will be performed using the methodology described in section 6.3.1. Summaries will be presented for the ITT Set in both groups.

6.3.3 Analyses for Primary Outcome

Primary outcome analysis will be conducted with a logistic generalized linear mixed model (GLMM) for repeated measures. Responder or non-responder at each scheduled post-baseline visit (end of treatment, and 20 and 24 weeks after treatment) is the dependent variable. Subjects who discontinue without providing the NIH-CPSI score will be considered as non-responders. The logistic GLMM is fitted using the logit link and the binomial distribution. The model will include the baseline NIH-CPSI total score as a fixed-effect covariate, with treatment group (acupuncture and sham acupuncture), visit and treatment \times visit interaction as fixed-effect categorical factors. The interaction will remain in the model regardless of significance. Treatment group comparisons at each visit will be estimated by differences between least squares means from the treatment \times visit interaction, and will be presented as odds ratios with accompanying *p* values and 95% CIs. The predicted probability of response at each visit will also be presented. Such models provide fairly robust results for treatment comparisons when longitudinal binary responses are missing, with an assumption that data are missing at random(MAR), according to reported values³⁶.

Sensitivity Analyses for the Primary Outcome

Because the MAR assumption cannot be verified using the data, the sensitivity of inferences to departures from the MAR assumption should be tested³⁷. A straightforward sensitivity analysis for the MAR assumption in multiple imputation is based on the control-based pattern imputation model under the MNAR assumption by using the SAS procedure Proc MI process. Therefore, mixed-effect model under MNAR assumption will be used. 6.3.4 Analyses for Secondary Outcome

Efficacy analyses for all secondary outcomes will be performed in the ITT population, without imputation of missing data.

Continuous data will be described with the average, standard deviation, median, minimum value, and maximum value, whereas categorical data will be represented by percentages as appropriate. Changes from baseline in the NIH-CPSI total score will be analyzed using linear mixed-effects model. The model will include the observed change from baseline score at each assessment point as the dependent variable; the baseline value, treatment group (acupuncture and sham acupuncture), visit and treatment \times visit interaction as fixed effects. Treatment group comparisons at each visit will be estimated by differences between least squares means from the treatment \times visit interaction, with accompanying *p* values and 95% CIs. Log-transformation may be applied in the case of serious violations of the model assumptions (normality and constant variance of the residuals). If not appropriate, the Wilcoxon rank-sum test will be used. The effect of the treatment will be estimated by the difference (or ratio, in the case of log-transformation) between treatments and will be presented along with its associated 95% CI. The same

approach will be used in other longitudinal continuous outcomes such as NIH-CPSI subscale scores (pain, urinary symptoms, and QoL).

Other categorical data or ordinal data will be compared between groups using the Wilcoxon rank-sum test, chi-square test or Fisher's exact test, as appropriate. The James and Bang blinding indices will be used to assess the success of blinding. The James blinding index is a variation on the statistic in which 1 represents perfect blinding. The Bang blinding index for each group represents the proportion of participants making a correct treatment guess beyond chance; 0 represents perfect blinding, a positive index indicates a correct guess, and a negative index indicates a guess in the opposite direction.

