3.3 Study Design and Organizations

This is a multicenter, participants-blinded, parallel-group, randomized controlled study conducted in China.

The participants will be recruited in 10 clinical sites, which are Dongfang Hospital Beijing University of Chinese Medicine; Beijing Fengtai Hospital of Integrated Traditional and Western Medicine; West China Hospital of Sichuan University; The Third Affiliated Hospital of Zhejiang Chinese Medical University; The First Affiliated Hospital of Anhui University of Chinese Medicine; Hengyang Hospital Affiliated to Hunan University of Chinese Medicine; The First Hospital of Hunan University of Chinese Medicine; Guangdong Provincial Hospital of Traditional Chinese Medicine; Yantai Hospital of Traditional Chinese Medicine; and Shaanxi Provincial Hospital of Traditional Chinese Medicine. Guang'anmen Hospital, China Academy of Chinese Medical Sciences will be responsible for study design and organization. A data coordination center will be established at China Academy of Chinese Medical Sciences (CACMS) to monitor data management.

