6.1 Randomization

In this study, we will use permuted blocks randomization, stratified according to center. A web-response system of Central Randomization System for Clinical Research (designed by Clinical Evaluation Center, China Academy of Chinese Medical Sciences) will be applied in our trial. The allocation sequence will be generated by Institute of Basic Research in Clinical Medicine, China Academy of Chinese Medical Sciences using statistical analysis software SAS 9.4 with "proc plan" program. After production, the sequence will be signed and sealed by the staff who produce it and kept by other staff who take no part in this trial. It will not be allowed to be checked by anyone except the top system administrator.

Only acupuncturists in each center will have access to random numbers and group allocation prior to treatment through the web. Participants will be randomly assigned to the acupuncture or sham acupuncture group at 1:1 ratio.

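### Randomisation is stratified by centre but no analysis includes centre; if centres differ in response, standard errors are too wide and some power is lost

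*Combined protocol and SAP*

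**What the plan says.** On allocation, protocol section 6.1 states that "we will use permuted blocks randomization, stratified according to center", with a 1:1 ratio. Section 3.3 states that "The participants will be recruited in 10 clinical sites".

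On the primary analysis, SAP section 6.3.3 specifies a logistic generalised linear mixed model for repeated measures. Its terms are given as "The model will include the baseline NIH-CPSI total score as a fixed-effect covariate, with treatment group (acupuncture and sham acupuncture), visit and treatment" by visit interaction. For change in NIH-CPSI total score and the other longitudinal continuous outcomes, SAP section 6.3.4 specifies a linear mixed model with "the baseline value, treatment group (acupuncture and sham acupuncture), visit and treatment" by visit interaction.

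Other categorical and ordinal outcomes are compared with ordinary Wilcoxon, chi-square or Fisher tests (SAP 6.3.1 and 6.3.4). Centre is not mentioned in the SAP's analysis sections as a fixed effect, random effect, stratum or sensitivity analysis, and no reason is given for leaving it out.

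**The concern.** Blocking within centre balances the arms in each centre, so differences between centres largely cancel out of the treatment contrast. An analysis that leaves centre out does not know this. It puts the between-centre variation into the residual (or into the subject effect) and charges it to the treatment comparison. The estimated variance is then larger than the real one, confidence intervals are wider than they need be, and the test rejects too seldom.

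Centre differences are plausible here. Each site has its own two acupuncturists, who treat both arms by hand, and the outcome is self-reported under that site's staff.

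Power is at stake rather than false positives. Protocol section 11.1 requires both week 8 and week 32 to be positive, so joint power is already below the 90% planned for a single comparison.

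**Working it through.** **Inputs.** Protocol 11.1 plans for "90% power to detect a difference of 17% between response rates in the two groups". The assumed rates there are 63.7% (acupuncture) and 46.7% (sham), with two-sided alpha 0.05, 15% added for dropouts and 440 in total. Protocol 3.3: 10 centres. Assumed, because the documents are silent: the between-centre variance, equal centre sizes and, for the mixed model, a subject random intercept with SD 2 on the logit scale.

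**1. The plan's own sample size.** With p̄ = 0.552 and d = 0.17,

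n = [1.960·√(2·0.552·0.448) + 1.282·√(0.637·0.363 + 0.467·0.533)]² / 0.17² = 177.7.

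With continuity correction, n_c = (177.7/4)·[1 + √(1 + 4/(177.7·0.17))]² = 189.3, so 190 per arm. Then 190 × 1.15 = 218.5, rounded to 219 per arm or 438 in total, against 440 stated. The figure reproduces. It comes from an unstratified formula, so adding centre does not change it. The 190 evaluable per arm is 19 per arm in each of 10 centres.

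**2. Linear models: algebra.** With balance inside each centre, the true variance of the treatment difference contains only within-centre variance, while the unadjusted model uses total variance. Hence reported SE / true SE = r = 1/√(1 − ICC). Actual type I error is 2[1 − Φ(1.96 r)]. For a comparison sized at 90% by the formula that ignores centre, power is Φ(1.282 r) without centre and Φ(3.242 r − 1.96) with it.

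| ICC (assumed) | r | Type I error without centre | Power without → with centre |
|---|---|---|---|
| 0.02 | 1.010 | 4.8% | 90.2% → 90.6% |
| 0.05 | 1.026 | 4.4% | 90.6% → 91.4% |
| 0.10 | 1.054 | 3.9% | 91.2% → 92.7% |
| 0.15 | 1.085 | 3.4% | 91.8% → 94.0% |

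**3. Responder outcome at one time point: simulation.** 40,000 trials per setting, 19 per arm in each of 10 centres, pooled two-proportion z test against the Mantel-Haenszel test stratified by centre.

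| Between-centre SD (logit) | Type I error without / with centre | Power without / with centre |
|---|---|---|
| 0 | – | 91.8% / 91.7% |
| 0.5 | 4.2% / 5.0% | 92.3% / 93.1% |
| 1.0 | 3.2% / 5.1% | 93.2% / 95.4% |

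A repeat run moved no figure by more than 0.2 points. In latent-scale terms, SD 0.5 is an ICC of 0.25/(0.25 + π²/3) = 0.07, and SD 1.0 is 1/(1 + π²/3) = 0.23.

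**4. The SAP's type of model: simulation.** Logistic mixed model with subject intercept, three visits, 190 per arm, 1,500 trials per setting, centre omitted or added as a fixed effect. The baseline score was left out.

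| ICC (assumed) | Mean model SE, week 8 | Power, week 8 | Power, both time points |
|---|---|---|---|
| 0 | 0.350 → 0.348 | 92.4% → 92.8% | 86.4% → 87.3% |
| 0.02 | 0.353 → 0.349 | 91.5% → 92.1% | 85.8% → 86.9% |
| 0.05 | 0.361 → 0.353 | 92.7% → 93.5% | 86.7% → 87.5% |
| 0.10 | 0.371 → 0.357 | 92.3% → 93.5% | 86.6% → 88.5% |
| 0.15 | 0.381 → 0.362 | 92.5% → 93.7% | 86.4% → 88.5% |

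At ICC 0.15 the mean estimate (1.243) is the same with and without centre, and its actual spread is nearly so (0.367 and 0.366). Only the reported SE changes, from 0.381 to 0.362. Under the null at that ICC, the model without centre reports 0.372 against an actual spread of 0.356, with type I error 3.8%; with centre it is 5.0%.

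Two cautions apply. The gain of 0.4 and 0.9 points at ICC 0 is not due to centre variation, so the raw gains slightly overstate the benefit. Simulation error is about 0.6 points on type I error and 0.7 on power, though both models were fitted to the same data sets. At ICC 0.10, type I error was 5.1% without centre and 6.0% with it, so the null results at intermediate ICCs do not separate the two models cleanly.

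**5. Joint power.** At 190 per arm, power for one time point is 91.8%. If the two tests were independent, joint power would be 0.918² = 84%; at a correlation of 0.9 it is about 89%.

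**The case against.** The loss is conditional and small. With no between-centre variation there is none, and the documents supply no variance from which to predict one. The protocol works to make sites alike, through common stepwise procedures, launch training, a video and centrally supplied needles (protocol 7.3). An SD of 1.0 is extreme: around a 46.7% response rate, centres one SD either side would respond at about 24% and 70%. In the one-time-point simulation, power without centre never fell below 91.8%, above the planned 90%. The joint-power shortfall is a separate matter that adding centre does not cure (88.5% at ICC 0.10 is still below 90%). All of this stands, and it is why the point is a recommended improvement and not a threat to validity.

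The phrase "too wide" also needs care in a logistic model. In a single-visit logistic regression at ICC 0.05, adding centre raises the SE of the log odds ratio from 0.211 to 0.218, because the estimate itself moves away from zero (non-collapsibility); power still rises, from 91.9% to 92.8%. The exact statement is that the reported SE is too wide relative to the true sampling variability.

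Finally, the terms in SAP 6.3.3 are fixed effects and no random effects are stated, so a centre random intercept could be called unspecified rather than excluded. Nothing in the text supports that reading: centre is absent from the analysis sections, and the other tests are plainly unstratified.

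**Conclusion.** The concern holds. The trial randomises within centre and analyses as if it had not. The error is in the conservative direction: type I error is not inflated and the sample size of 440 is unaffected. Over an assumed ICC of 0 to 0.15 the cost is about 0 to 2 points of power at one time point, and the raw gain for both time points together is about 1 to 2 points. At a between-centre SD of 1.0 it reaches 2.2 points, with type I error down to 3.2%. These sizes depend on the assumed centre variation, equal centre sizes and, for the mixed model, the assumed subject effect. The direction does not depend on the particular values, provided centres differ at all. The change should be made, because the loss is avoidable in a trial that needs two positive results.

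**What to change.** Before the SAP is finalised and while the data are still blinded (protocol 10.4.7 and 11.2):

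- Add centre to the logistic and linear mixed models, as a 10-level fixed effect (nine parameters) or a random intercept, and carry it into the sensitivity analysis of the primary outcome.
- State the random effects of both models in full, including the subject effect.
- State that the odds ratio is then conditional on centre, and how the predicted response probabilities are averaged over centres.
- For the other categorical and ordinal outcomes, use the Cochran-Mantel-Haenszel and van Elteren tests stratified by centre.
- If centre is fitted as a fixed effect, set a rule now for pooling centres with very few participants.

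If centre is to be left out, the SAP should give the reason. The cost is one term per model and a stratified version of each test. No new data are needed. Settling it now also removes a later choice between adjusted and unadjusted results.
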